10.2 Recording Adverse Events

CTCAE term (AE description) and grade: The descriptions and grading scales found in the revised NCI Common Terminology Criteria for Adverse Events

(CTCAE) version 5.0 will be utilized for AE reporting unless as otherwise stated in the table below.

All appropriate treatment areas should have access to a copy of the CTCAE version 5.0. A copy of the CTCAE version 5.0 can be downloaded from the CTEP web site:

(http://ctep.cancer.gov/protocolDevelopment/electronic_applications/ctc.htm)

10.2.1 Adverse event monitoring and reporting is a routine part of every clinical trial. First, identify and grade the severity of the event using the CTCAE version 5.0. Next, determine whether the event is expected or unexpected and if the adverse event is related to the medical treatment or procedure. With this information, determine whether the event must be reported as an expedited report (see Section 10.3).

10.2.2 Assessment of Attribution

Only G4 or G5 adverse events will require an attribution. Any change in the grade of an adverse event within the list of monitored AEs will be recorded and considered to be related to treatment. Any new adverse not listed occurring within the radiated area or in close proximity will be graded and attribution defined by the study PI.

Events determined to be possibly, probably or definitely attributed to a medical treatment suggest there is evidence to indicate a causal relationship between the treatment and the adverse event.

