10.5 Submit via appropriate *reporting mechanisms* the following AEs experienced by a patient through the course of Radiation Therapy and not specified in Section 10.4:

10.5.1 Grade 3, 4, and 5 AEs regardless of attribution to the study treatment or procedure.

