16.4 Data Safety and Monitoring

16.4.1 Safety Review: The principal investigator(s) and the study statistician will review the study monthly to identify accrual, adverse event, and any endpoint problems that might be developing. The Mayo Clinic Cancer Center (MCCC) Data Safety Monitoring Board (DSMB) is responsible for reviewing accrual and safety data for this trial at least biannually, based on reports provided by the MCCC Statistical Office.

16.4.2 Adverse Event Stopping Rules: The stopping rule specified below is based on the knowledge available at study development. We note that the Adverse Event Stopping Rule may be adjusted in the event of either (1) the study re-opening to accrual or (2) at any time during the conduct of the trial and in consideration of newly acquired information regarding the adverse event profile of the treatment(s) under investigation. The study team may choose to suspend accrual because of unexpected adverse event profiles that have not crossed the specified rule below.

Accrual may be temporarily suspended to this study if at any time we observe events considered at least possibly related to Radiation Therapy (i.e., an adverse event with attribute specified as “possible”, “probable”, or “definite”) that satisfy one of the following:

- If 8 or more of the first 20 patients (or 40% or more of all patients after 10 are accrued) experience a Grade 3+ AE.
- If 4 or more experience a Grade 5 AE at any time.

After consideration by the study team (Study Chair, statistician, etc.), a decision will be made as to whether accrual can be resumed. In addition, we will review grade 4 and 5 adverse events deemed “unrelated” or “unlikely to be related”, to verify their attribution and to monitor the emergence of a previously unrecognized treatment-related adverse event.

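### The accrual-suspension rule needs a radiation attribution for Grade 3 events, but Section 10.2.2 requires attribution only for Grades 4 and 5, so the text does not determine the Grade 3 count

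*Combined protocol and SAP*

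**What the plan says.** Section 16.4.2 sets the trial's only numerical adverse-event suspension rule: "Accrual may be temporarily suspended to this study if at any time we observe events considered at least possibly related to Radiation Therapy". It spells this out as an attribution recorded as possible, probable or definite. The first limb is met when 8 or more of the first 20 patients, or 40% or more of all patients after 10 are accrued, have such an event at Grade 3 or above. The second limb is 4 or more Grade 5 events. The same section has the team re-check events called unrelated or unlikely, but only at Grades 4 and 5.

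Section 10.2.2 says which events get an attribution. Its first sentence is "Only G4 or G5 adverse events will require an attribution". Two further sentences carry no grade limit. For solicited events: "Any change in the grade of an adverse event within the list of monitored AEs will be recorded and considered to be related to treatment". For the rest: "Any new adverse not listed occurring within the radiated area or in close proximity will be graded and attribution defined by the study PI".

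Three other places bear on the point. Section 10.2.1 tells staff to "determine whether the event is expected or unexpected and if the adverse event is related to the medical treatment or procedure". Section 10.5.1 has unlisted events during the radiation course submitted if they are "Grade 3, 4, and 5 AEs regardless of attribution to the study treatment or procedure". The joint stiffness form (Appendix IV) records attribution to radiation and to surgery separately, each on a five-level scale, whatever the grade.

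**The concern.** The rule's numerator is defined by two fields, grade and attribution to radiation. It starts at Grade 3, and Grade 3 is where 10.2.2 stops requiring the second field. If that sentence is followed literally, part of the input is never collected. If the sentence on listed events is followed instead, events enter the count with no judgement about radiation at all.

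Two teams working from this text could therefore reach different Grade 3 counts from the same patients. At stake is whether accrual is paused for a team review when the rule intends it, and not otherwise.

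**Working it through.** **1. The plan's own figure.** 8/20 = 0.40, which matches the stated 40%. The two parts of the first limb agree at patient 20, and the boundary itself is not in question.

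**2. What each class of Grade 3 event receives.** The rule needs a category of relation to radiation therapy.

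| Grade 3 event | What the text supplies | Gap against 16.4.2 |
|---|---|---|
| Listed (10.4) | Any grade change is deemed related to treatment (10.2.2) | No category. Treatment is not narrowed to radiation: Section 7.0, on protocol treatment, also covers surgery and chemotherapy. Disease is not separated: fatigue and tumor pain are listed acute events. |
| Unlisted, in or near the field | The study PI defines attribution (10.2.2) | Apparent conflict with the first sentence of 10.2.2, which requires none below Grade 4 |
| Unlisted, away from the field, during radiation | Submitted whatever the attribution (10.5.1); general relatedness step (10.2.1) | No attribution category required |
| Joint stiffness | Five-level attribution to radiation (Appendix IV) | None |

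The first class can push the count up, the third can push it down, and the second depends on which sentence of 10.2.2 a team follows.

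**3. How sensitive the rule is to the count.** The documents give neither the true rate nor the share of events affected, so every rate here is an assumption. Let q be the proportion of patients counted.

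- First 20 patients: P(X ≥ 8) = Σ from k = 8 to 20 of C(20,k) q^k (1−q)^(20−k).
- Ever crossing by patient 120: the number counted, k, rises by 1 with probability q at each patient, and the path stops when k ≥ 8 within the first 20 or k ≥ 0.4i at patient i. The 40% check starts at patient 11 (lower figure) or patient 10 (higher figure), since the wording allows either. Outcomes are taken as known in order of accrual.

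| Counted rate q | P(8 or more of first 20) | P(ever crossing by 120) |
|---|---|---|
| 0.20 | 0.032 | 0.100–0.148 |
| 0.30 | 0.228 | 0.434–0.490 |
| 0.36 | 0.436 | 0.729–0.760 |
| 0.40 | 0.584 | 0.887–0.901 |

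*Under-counting.* Take a true radiation-related rate of 0.40 and let a fraction f of affected patients carry a countable attribution, so q = 0.40 × f. With f = 1, 0.9, 0.75 and 0.5, q = 0.40, 0.36, 0.30 and 0.20. The chance in the first 20 falls from 0.584 to 0.436, 0.228 and 0.032.

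*Over-counting.* Take a true radiation-related rate of 0.20 and suppose a further 0.10 of patients are counted only because a listed event with another cause is deemed related. Then q = 0.20 + 0.10 = 0.30, and the chance in the first 20 rises from 0.032 to 0.228.

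These rows show sensitivity only; they do not estimate what will happen in this trial.

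**The case against.** The strongest case against is that 10.2.2 does not stop at its first sentence. A listed Grade 3 change is deemed related, which meets the plain sense of "if at any time we observe events considered at least possibly related to Radiation Therapy". An unlisted event in or near the field goes to the PI. Radiation acts locally, so these two classes should cover most of what the rule is meant to catch. Section 10.2.1 asks about relatedness at any grade, and the example adverse-event worksheet in 10.3.1 has a relationship field. Deeming solicited events related is a defensible convention in a single-arm trial and errs toward triggering review. The rule is also not the only safeguard: 16.4 provides monthly review by the PI and statistician and at least biannual DSMB review, and lets the team suspend accrual before the boundary is crossed.

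Much of this stands. A reader might infer that the rule cannot count Grade 3 events at all, sees only Grades 4 and 5, and would almost never trigger. The documents do not support that reading, because it ignores the two sentences that assign relatedness without a grade limit. Any trigger probability built on it would also need Grade 4–5 rates that the documents do not give.

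What the objection does not supply is the rule's own variable. Being related to treatment is not a category of relation to radiation. The worksheet is labelled an example. The general step in 10.2.1 names treatment or procedure, and 10.2.2 then narrows what is required. Appendix IV covers one toxicity.

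**Conclusion.** The conflict is real and should be fixed. It is a contradiction between two stated rules, and it leaves the Grade 3 count dependent on which sentence a team follows. The error could go either way. The share of events affected is not in the documents; the class left with no required category, unlisted Grade 3 events away from the field, is probably the smallest. The illustration shows that the share would matter if the true rate were near the boundary: at an assumed 40%, missing a quarter of affected patients takes the chance of 8 or more in the first 20 from 0.584 to 0.228. The Grade 5 limb is unaffected, because Grade 5 events do require an attribution. Nothing here bears on the primary endpoint or the sample size.

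**What to change.** Reconcile the two sections.

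- Amend 10.2.2 to require attribution to radiation therapy for every Grade 3, 4 and 5 event, listed or not, on the five-level scale already used in Appendix IV (definite, probable, possible, unlikely, unrelated).
- State in 16.4.2 how a listed event deemed related to treatment enters the count. The automatic convention can stay if the section says so explicitly; the point does not depend on removing it.

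The boundary needs no change for this purpose. The cost is a short amendment, one extra eCRF field for Grade 3 events and a little investigator time.

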10.3 Reporting of Serious Adverse Events and Unanticipated Problems

When an adverse event has been identified, the study team will take appropriated action necessary to protect the study participant and then complete the Study Adverse Event Worksheet and log. The sponsor-investigator will evaluate the event and determine the necessary follow-up and reporting required.

- a. Serious Adverse Events will be reported as part of regular adverse event reporting mechanisms via the data capture system and logged for review reporting.

10.3.1 Investigator Reporting: Notifying the Mayo IRB

The IRB requirements reflect the guidance documents released by the Office of Human Research Protections (OHRP), and the Food and Drug Administration (FDA) in early 2007 and are respectively entitled “Guidance on Reviewing and Reporting Unanticipated Problems Involving Risks to Subjects or Others and Adverse Events” and “Guidance for Clinical Investigators, Sponsors, and IRBs: Adverse Event Reporting – Improving Human Subject Protection.”

- 10.3.1.1 According to Mayo IRB Policy any serious adverse event (SAE) which the Principal Investigator has determined to be a UPIRTSO must be reported to the Mayo IRB as soon

- 10.3.1.2 as possible but no later than 5 working days after the investigator first learns of the problem/event.
Non-UPIRTSO – the investigator reports problems or events that do NOT meet criteria of an UPIRTSO in summary format at the time of the next continuing review. The investigator monitors the severity and frequency of subsequent non-UPIRTSOs.

Consider the following information to collect when developing any forms for documentation of adverse events.

Example

Information collected on the adverse event worksheet (and entered in the research database):

- Subject's name:
- Medical record number:
- Disease/histology (if applicable):
- The date the adverse event occurred:
- Description of the adverse event:
- Relationship of the adverse event to the research (drug, procedure, or intervention):
- If the adverse event was expected:
- The severity of the adverse event: (use a table to define severity scale 1-5)
- If any intervention was necessary:
- Resolution: (was the incident resolved spontaneously, or after discontinuing treatment)
- Date of Resolution:

The investigator will review all adverse event reports to determine if specific reports need to be made to the IRB and FDA. The investigator will sign and date the adverse event report when it is reviewed. For this protocol, only directly related SAEs/UPIRTSOs will be reported to the IRB.

- 10.4 Solicited toxicities to be graded at each evaluation and pretreatment symptoms/conditions to be evaluated based on the schedule of events using the CTCAE v5.0 grading unless otherwise stated in the table below. This regimen has established safety, based on this article [https://www.thelancet.com/journals/lanonc/article/PIIS1470-2045\(22\)00638-6/fulltext](https://www.thelancet.com/journals/lanonc/article/PIIS1470-2045(22)00638-6/fulltext) so the focus is on solicited toxicities and not any adverse event after radiation therapy is completed.

ACUTE TOXICITIES – Upper Proximal Extremity			
CTCAE System/Organ/Class (SOC)	Adverse Event / Symptoms	Baseline	During RT & Preoperative Assessment

General disorders and administration site conditions	Fatigue	X	X
Skin and subcutaneous tissue disorders	Dermatitis Radiation	X	X
	Hyperpigmentation	X	X
Neoplasm benign, malignant and unspecified	Tumor pain	X	X

LATE TOXICITIES – Upper Proximal Extremity		
CTCAE System/Organ/Class (SOC)	Adverse Event / Symptoms	Post-Surgery & Follow Up
Skin and subcutaneous tissue disorders	Hyperpigmentation ¹	X
Vascular	Lymphedema ²	X
General disorders and administration site conditions	Localized edema ¹	X
Musculoskeletal and connective tissue disorders	Fibrosis deep connective tissue ¹	X
	Joint range of motion decreased ²	X
	Osteonecrosis ¹	X

Neoplasm benign, malignant and unspecified	Tumor pain ¹	X
Injury, poisoning and procedural complications	Fracture ¹	X
Gastrointestinal Disorders ¹	Esophageal fistula	X
Respiratory, thoracic and mediastinal disorders	Pneumonitis ¹	X

¹ Specific to radiation / surgery treatment area

² Specific to ipsilateral extremity / region

ACUTE TOXICITIES – Upper Distal Extremity (includes elbow)			
CTCAE System/Organ/Class (SOC)	Adverse Event / Symptoms	Baseline	During RT & Preoperative Assessment
General disorders and administration site conditions	Fatigue	X	X
Skin and subcutaneous tissue disorders	Dermatitis Radiation	X	X
	Hyperpigmentation	X	X
Neoplasm benign, malignant and unspecified	Tumor pain	X	X

LATE TOXICITIES – Upper Distal Extremity (includes elbow)		
CTCAE System/Organ/Class (SOC)	Adverse Event / Symptoms	Post-Surgery & Follow Up
Skin and subcutaneous tissue disorders	Hyperpigmentation ¹	X
Vascular	Lymphedema ²	X
General disorders and administration site conditions	Localized edema ¹	X
Musculoskeletal and connective tissue disorders	Fibrosis deep connective tissue ¹	X
	Joint range of motion decreased ²	X
	Osteonecrosis ¹	X
Neoplasm benign, malignant and unspecified	Tumor pain ¹	X
Injury, poisoning and procedural complications	Fracture ¹	X

¹ Specific to radiation / surgery treatment area

² Specific to ipsilateral extremity / region

ACUTE TOXICITIES – Lower Proximal Extremity (includes knee)			
CTCAE System/Organ/Class (SOC)	Adverse Event / Symptoms	Baseline	During RT & Preoperative Assessment
General disorders and administration site conditions	Fatigue	X	X

Skin and subcutaneous tissue disorders	Dermatitis Radiation	X	X
	Hyperpigmentation	X	X
Gastrointestinal disorders	Diarrhea	X	X
	Nausea	X	X
	Vomiting	X	X
Renal and urinary disorders	Dysuria	X	X
Neoplasm benign, malignant and unspecified	Tumor pain	X	X

LATE TOXICITIES – Lower Proximal Extremity (includes knee)		
CTCAE System/Organ/Class (SOC)	Adverse Event / Symptoms	Post-Surgery & Follow Up
Skin and subcutaneous tissue disorders	Hyperpigmentation ¹	X
Vascular	Lymphedema ²	X
General disorders and administration site conditions	Localized edema ¹	X
	Fibrosis deep connective tissue ¹	X

Musculoskeletal and connective tissue disorders	Joint range of motion decreased ²	X
	Osteonecrosis ¹	X
Neoplasm benign, malignant and unspecified	Tumor pain ¹	X
Injury, poisoning and procedural complications	Fracture ¹	X
Gastrointestinal Disorders ¹	Anal fistula	X
	Colonic fistula	X
	Duodenal fistula	X
	Ileal fistula	X
	Jejunal fistula	X
	Rectal fistula	X
	Anal ulcer	X
	Colonic ulcer	X
	Duodenal ulcer	X
	Ileal ulcer	X
	Jejunal ulcer	X
	Rectal ulcer	X
	Small intestine ulcer	X
	Anal stenosis	X
	Colonic stenosis	X
	Duodenal stenosis	X

	Ileal stenosis	X
	Jejunal stenosis	X
	Rectal stenosis	X
	Small intestine stenosis	X
	Rectal perforation	X
	Small intestine perforation	X
	Colonic perforation	X
	Duodenal perforation	X
	Ileal perforation	X
	Jejunal perforation	X
	Enterovesical fistula	X
	Renal and urinary disorders ¹	X
	Bladder perforation	X

¹ Specific to radiation / surgery treatment area

² Specific to ipsilateral extremity / region

ACUTE TOXICITIES – Lower Distal Extremity			
CTCAE System/Organ/Class (SOC)	Adverse Event / Symptoms	Baseline	During RT & Preoperative Assessment

General disorders and administration site conditions	Fatigue	X	X
Skin and subcutaneous tissue disorders	Dermatitis Radiation	X	X
	Hyperpigmentation	X	X
Neoplasm benign, malignant and unspecified	Tumor pain	X	X

¹ Per study definition

LATE TOXICITIES – Lower Distal Extremity		
CTCAE System/Organ/Class (SOC)	Adverse Event / Symptoms	Post-Surgery & Follow Up
Skin and subcutaneous tissue disorders	Hyperpigmentation ¹	X
Vascular	Lymphedema ²	X
General disorders and administration site conditions	Localized edema ¹	X
Musculoskeletal and connective tissue disorders	Fibrosis deep connective tissue ¹	X
	Joint range of motion decreased ²	X
	Osteonecrosis ¹	X

Neoplasm benign, malignant and unspecified	Tumor pain ¹	X
Injury, poisoning and procedural complications	Fracture ¹	X

¹ Specific to radiation / surgery treatment area

² Specific to ipsilateral extremity / region

ACUTE TOXICITIES – Superficial Trunk			
CTCAE System/Organ/Class (SOC)	Adverse Event / Symptoms	Baseline	During RT & Preoperative Assessment
General disorders and administration site conditions	Fatigue	X	X
Skin and subcutaneous tissue disorders	Dermatitis Radiation	X	X
	Hyperpigmentation	X	X
Gastrointestinal disorders	Diarrhea	X	X
	Nausea	X	X
	Vomiting	X	X
Renal and urinary disorders	Dysuria	X	X
Neoplasm benign, malignant and unspecified	Tumor pain	X	X

LATE TOXICITIES		
CTCAE System/Organ/Class (SOC)	Adverse Event / Symptoms	Post-Surgery & Follow Up
Skin and subcutaneous tissue disorders	Hyperpigmentation ¹	X
General disorders and administration site conditions	Localized edema ¹	X
	Lymphedema	X
Musculoskeletal and connective tissue disorders	Fibrosis deep connective tissue ¹	X
	Joint range of motion decreased ²	X
	Osteonecrosis ¹	X
Neoplasm benign, malignant and unspecified	Tumor pain ¹	X
Injury, poisoning and procedural complications	Fracture ¹	X
Gastrointestinal Disorders ¹	Anal fistula	X
	Colonic fistula	X
	Duodenal fistula	X
	Esophageal fistula	X
	Gastric fistula	X
	Ileal fistula	X
	Jejunal fistula	X

	Rectal fistula	X
	Anal ulcer	X
	Colonic ulcer	X
	Duodenal ulcer	X
	Gastric ulcer	X
	Ileal ulcer	X
	Jejunal ulcer	X
	Rectal ulcer	X
	Small intestine ulcer	X
	Anal stenosis	X
	Colonic stenosis	X
	Duodenal stenosis	X
	Gastric stenosis	X
	Ileal stenosis	X
	Jejunal stenosis	X
	Rectal stenosis	X
	Small intestine stenosis	X
	Rectal perforation	X
	Small intestine perforation	X
	Colonic perforation	X
	Duodenal perforation	X
	Gastric perforation	X
	Ileal perforation	X

	Jejunal perforation	X
	Enterovesical fistula	X
Renal and urinary disorders ¹	Urinary fistula	X
	Bladder perforation	X
Respiratory, thoracic and mediastinal disorders	Pneumonitis ¹	X

¹ Specific to radiation / surgery treatment area

² Specific to ipsilateral extremity / region

10.5 Submit via appropriate *reporting mechanisms* the following AEs experienced by a patient through the course of Radiation Therapy and not specified in Section 10.4:

10.5.1 Grade 3, 4, and 5 AEs regardless of attribution to the study treatment or procedure.

10.5.2 Grade 5 AEs (Death)

10.5.2.1 Any death within 30 days of the patient's last study treatment or procedure regardless of attribution to the study treatment or procedure

10.5.2.2 Any death more than 30 days after the patient's last study treatment or procedure that is felt to be at least possibly treatment related must also be submitted as a Grade 5 AE, with a CTCAE type and attribution assigned.

10.6 Monitoring and Auditing

The investigator will permit study-related monitoring, audits, and inspections by the IRB, the sponsor, and government regulatory agencies, of all study related documents (e.g. source documents, regulatory documents, data collection instruments, study data etc.). The investigator will ensure the capability for inspections of applicable study-related facilities (e.g. pharmacy, diagnostic laboratory, etc.). Participation as an investigator in this study implies acceptance of potential inspection by government regulatory authorities and applicable compliance offices.

10.6.1 Medical Monitoring

It is the responsibility of the Principal Investigator to oversee the safety of the study at his/her site. This safety monitoring will include careful assessment and appropriate reporting of adverse events as noted above, as well as the construction and implementation of a site data and safety-monitoring plan (see section 10.5 “Monitoring and Auditing”). Medical monitoring will include a regular assessment of the number and type of serious adverse events. Any serious adverse events will be followed up by the sentinel event reporting procedure.

10.6.2 Internal Data and Safety Monitoring Board

The trial will be reviewed by the Cancer Center Auditing area on a bi-annual or yearly basis dependent on random study selection to assess accrual, adverse events, and any endpoint problems. Any safety issues requiring protocol changes will be communicated through protocol amendments.

11.0 Treatment Evaluation/Measurement of Effect

- 11.1 Development of a surgical wound complication: Secondary unplanned operation under general or regional anesthesia for wound repair (e.g., debridement, operative drainage, or secondary wound closure including rotationplasty, free flaps or skin grafts); or wound management without secondary operation including invasive procedures (e.g., aspiration of seroma or readmission for wound care such as intravenous antibiotics or persistent deep packing for 120 days or longer).
- 11.2 Local recurrence free survival: Any radiographic or pathologic evidence of recurrent disease inside the CTV and/or beyond the CTV to within a 3 cm distance from the edge of the CTV. Ideally assessed by radiographic imaging in comparison to the treatment fields in order to determine site of recurrence.

